## 9.0 Setting

**Directions: Describe the sites and locations where your research team will conduct the research.**

All research will be conducted at Case Western Reserve University where the study team has lab space to collect data by telephone, REDCap, and Zoom in a private space. Some data on app utilization will be collected by Amicus Brain Innovations for use by Case Western Reserve University researchers.

## 10.0 Consent Process

**Indicate whether you will be obtaining consent:**

Yes       No

**If yes, answer the following questions:**

1. Describe who will consent the subjects and where the consent process will take place: The consent process will be completed using an online consent form completed in REDCap, wherein participants will be asked to review a written consent form and answer 5 true or false questions about participation to check understanding. If these questions are not answered correctly, a study team member will contact the participant to clarify information and resend the consent form. If

answers are still incorrect, the participant will be deemed ineligible to participate and notified of their removal from the study.

2. The time that will be devoted to the consent discussion: The time to complete the online consent form will vary among participants, though we anticipate it will take no more than 1 hour and, for most participants, around 20 minutes.
3. Any waiting period available between informing the prospective subject and obtaining the consent: There is no required waiting period between informing the participant of their eligibility and the consenting process. However, participants may choose to delay consent following notification of eligibility, such as by taking additional time to complete the online consent form.
4. Steps that will be taken to ensure the research participants' understanding: Participants will be asked to complete 5 questions about what is involved in the study to ensure understanding of the written consent form. They may also contact members of the study team with any questions they may have.
5. Any process to ensure ongoing consent: We will assume ongoing consent if the participant chooses to complete surveys. At the top of each survey, participants will be reminded that participation is voluntary
6. Steps that will be taken to minimize the possibility of coercion or undue influence to the subjects: While consenting participants, we will remind them that participation is voluntary and that they are welcome to participate in CONFIDENCE regardless of their choice to participate in the research study

### **For Adult Participants**

**Indicate if you will be asking for a waiver or alteration of consent process or documentation (consent will not be obtained, or written consent will not be documented)**

Yes       No

**If yes**, explain how the research involves no more than minimal risk. We are requesting a waiver of consent related to provision of a signature for a sub-study, wherein we will ask caregivers who are not in the parent study to participate in a qualitative interview. The interview content focuses on their experience in the CONFIDENCE program and is aligned with the goals of program evaluation/quality improvement. It is unlikely private or embarrassing information would be shared.

**Indicate which part of the consent process you are requesting be waived or altered and the rationale for requesting the waiver or alteration:**

I will obtain consent, but not participant's signature.

1. Give the rationale for the request of a waiver of signed consent. Those individuals who did not enroll in the study are likely busier than those who are enrolled in the parent research study. Asking for a consent signature may add additional burden to a minimal-risk component of the study.
2. Please describe how you will be documenting that a participant has consented. The interviewer will ask the participant if they consent to participate at the beginning of the interview. They interview will not proceed unless consent is given
3. Indicate if the subjects will be provided with written information about the study, and provide justification if you will not be providing a written explanation of the research. Caregivers will be sent a copy of the information sheet prior to the scheduled interview, if they agree to be interviewed. This will be reviewed at the beginning of the interview.

I will obtain consent, but request a waiver of some of the elements of consent (e.g. use of deception).

I will not obtain any consent, and I am requesting a full waiver of consent.

**If you are requesting an alteration of consent, or a waiver of consent, please answer the following:**

1. Give the rationale for the request of a waiver or alteration of the consent process. See above
2. Explain why the waiver or alteration of consent will not adversely affect the rights and welfare of the participants. The questions asked in the qualitative interview are unlikely to result in disclosure of sensitive information, and are more aligned with the goals of program evaluation or quality improvement than research.
3. Explain why the research could not practicably be carried out without the waiver or alteration of consent. Requiring a signature would put additional burden on caregivers without necessarily reducing already minimal risks.
4. Indicate if the subjects will be provided with additional information about the study after participation. Caregivers will be provided additional

information at the end of the study, including a written summary and invitation to view a presentation about results

*\*Be sure to upload a consent script or information sheet with your study protocol*

### **Additional Considerations for Consent Process with Adults**

#### Non English Speakers *(Please select one)*

I am not enrolling non-English speaking individuals in this research study. The following is justification for why non-English speaking individuals cannot be enrolled: [Click here to enter text](#).

I will be targeting non-English speaking adults

1. Describe the process to ensure that the oral and written information provided to those research participants will be in that language during initial consent as well as throughout the study. Study, intervention, and communicative documents have been translated from the English version to Spanish by a professional translation service and checked by research assistants that are fluent/native in both English and Spanish languages. When available, we use validated translations of scales; for those scales that are not validated, we use forward and back translation with at least two study team members fluent in Spanish. Qualitative interviews will also be translated by a professional translation team (ASTA USA). Interventionists responsible for delivering the Spanish version of CONFIDENCE at the USC Family Caregiver Support Center are fluent in Spanish. Study team members who conduct enrollment of participants and review the consent process will also be native Spanish speakers. Three RAs have been hired to ensure sufficient coverage for this,
2. List the language(s) other than English that will be targeted: Spanish

I am not targeting non-English speaking individuals. If a non-English speaking individual is eligible for the study, we will use the following procedures to enroll:

1. Describe the process to ensure that the oral and written information provided to those research participants will be in that language during initial consent as well as throughout the study. [Click here to enter text](#).
2. List the language(s) other than English that will be targeted: [Click here to enter text](#).

#### Adults Unable to Consent

I am not enrolling adults unable to consent in this research study – *please leave the rest of this section blank*.

There is an anticipated direct benefit to the subject. Explain: [Click here to enter text](#).

There is NOT an anticipated direct benefit to the subject. Explain: [Click here to enter text.](#)

1. Describe the process to determine whether an individual is capable of consent. [Click here to enter text.](#)
2. List the individuals from whom permission will be obtained in order of priority (e.g. durable power of attorney for health care, court appointed guardian for health care decisions, spouse, and adult child). [Click here to enter text.](#)
3. For research conducted outside of the state, provide information that describes which individuals are authorized under applicable law to consent on behalf of a prospective subject to their participation in the procedure(s) involved in the research. [Click here to enter text.](#)
4. Describe the process for assent of the research participants. Indicate:
  - Which subjects that are unable to consent will be required to give assent? If not all, explain why. [Click here to enter text.](#)
  - Describe whether assent of the research participants will be documented and the process to document assent. [Click here to enter text.](#)

The subject will be informed about the research to the extent compatible with the subject's understanding.

Subjects will be closely monitored.

The subject will be withdrawn if they appear unduly distressed.

#### **Research Participants Who Are Not Yet Adults (infants, children, teenagers)**

I am not enrolling participants who are not yet adults in this research study. *– [please leave the rest of this section blank](#)*

1. Will parental permission be obtained from:
  - One parent even if the other parent is alive, known, competent, reasonably available, and shares legal responsibility for the care and custody of the child
  - Both parents unless one parent is deceased, unknown, incompetent, or not reasonably available, or when only one parent has legal responsibility for the care and custody of the child
  - Requesting a waiver of parental permission

#### **If you are getting parental/guardian permission:**

- a. Indicate how you will be documenting the permission:

- Signed consent form

Requesting a waiver of documentation of parental permission

b. Describe whether permission will be obtained from individuals other than parents, and if so, who will be allowed to provide permission. Describe the process used to determine these individuals' authority to consent to each child's participation in research. [Click here to enter text](#).

**If a waiver of parental permission is being requested:**

a. Describe how the study is designed for a subject population for which parental/guardian permission is not a reasonable requirement to protect the subjects, if applicable. [Click here to enter text](#).

b. Describe how the research could not practicably be carried out without the waiver of parental permission. [Click here to enter text](#).

c. Indicate if the subjects will be provided with additional information about the study after participation. [Click here to enter text](#).

2. Will assent be obtained from:

all of the children  
 some of the children  
 none of the children

If assent will be obtained from some children, indicate which children will be required to assent. [Click here to enter text](#).

If assent will be obtained from none of the children, indicate the rationale. [Click here to enter text](#).

When assent of children is obtained, describe how it will be documented. [Click here to enter text](#).

3. For children who are pregnant, describe how assent and permission are obtained. [Click here to enter text](#).

N/A

## 11.0 Sharing of Results with Research Participants

Individual test or research results will be shared with research participants (this is not referring to sharing through standard academic channels, e.g., publishing, presentation, etc.):

Yes       No

If yes, describe how the results will be shared. [Click here to enter text](#).

Individual test results will be shared with others (e.g., lab results given to a primary care physician):

Yes  No

If yes, describe with whom and how the results will be shared. [Click here to enter text.](#)

## 12.0 Study Design/Procedures

### Directions:

- 1) **Describe the overall study design (e.g.: single visit, single-blind, double-blind, non-randomized, randomized, blood draw, investigational drug, device etc.).**
- 2) **Provide a description of all study-related research procedures being performed, including the length of time involved.**
- 3) **Include procedures being performed to monitor research participants for safety or minimize risks.**
- 4) **Describe the source records including medical or educational records, which will be used to collect data about subjects.**
- 5) **Include a description of any device being used to collect data (e.g., eye tracker, step counter). If the device itself is being studied, include additional information in Section 29.**

**Overall design.** A single-arm pre- and post-test clinical trial of the CONFIDENCE intervention will be conducted. This study builds on the original CONFIDENCE study (STUDY20221010), but with a modified version of the intervention and minor updates in data collection protocols to reduce participant burden. Participation will be offered to any caregiver of persons living with dementia nationally who register for the program via the USC Family Caregiver Support Center (USC FCSC) Eventbrite. Study participation is optional. CONFIDENCE will be delivered in English and Spanish, and participants may participate in the study in either language.

**Intervention** The intervention includes participation in four, 1.5 hour group discussion sessions delivered by Family Consultants from the USC Family Caregiver Support Center. Zoom sessions will be attended by other caregivers and will feature vignette-style videos featuring family caregivers as well as peer-learning activities. Between the sessions, caregivers will receive text messages from NeuViCare™ with informational tips and reminders to complete practice exercises. They may also choose to interact with Keiko, the apps conversational AI assistant that generates responses to questions based on sources selected or created by the study team. Caregivers can also participant in a monitored community forum, wherein they will be able to communicate with other caregivers in the program. Participants will be sent instructions on how to register for the NeuViCare App, and will have a dedicated “NeuViCare champion” at the USC FCSC who they can turn to if they need additional support. Total time for intervention participation in 8 to 10 hours over 4 weeks.

**Recruitment strategy.** Caregivers will primarily be recruited from the USC FCSC by sending information about CONFIDENCE via email blast, as well as individual email invitations and follow-up calls sent to participants who are likely to be eligible for the study. The USC FCSC may also advertise this program via social media channels and with community partners, as they would any program they offer to the community. Caregivers may also learn about the study on the Alzheimer’s Association TrialMatch

site.

**Enrollment and consenting.** Participants who register on Eventbrite and are interested in learning about the study will receive up to four calls and emails by a study team member to learn more about the study. If interested in participating, eligibility screening and a review of the study consent information will be conducted by phone with the PI or a trained study team member. (Participants may complete the screening process online, but are asked to complete a telephone follow up where they will be asked the screening item about the Global Deterioration Scale and other questions they did not respond to.) Participants will then be sent an email with a REDCap consent form to review and signature. Total enrollment and consenting time is estimated to take up to 1 hour.

**Survey administration.** Once enrolled, participants will receive the baseline survey up to 3 weeks before their first CONFIDENCE session by email, which includes questions about spending on out-of-pocket care costs, financial strain, resourcefulness, self-efficacy, and information about the caregiving context and use of supports. The first follow-up survey will be sent immediately post-intervention (i.e., within 1 week). A second follow-up survey will be sent two months following intervention completion to understand the maintenance of outcomes. We estimate follow up surveys take about 30 to 45 minutes to complete.

**Qualitative interviews.** In-depth, open-ended, semi-structured qualitative interviews will be conducted with at least 12 participants by phone and/or Zoom, both in Spanish and English. Questions will be based on caregiver's experiences and opinions about their participation in CONFIDENCE 2. The interview guide will be based on the seven components of the Theoretical Framework of Acceptability. This guide will be previously reviewed by an advisory council. Questions about the theory of resourcefulness will be also included to better understand its application. Depending on how much participants would like to share, we estimate interviews will last 15 minutes to 1 hour. Update 9/2/2024: The research team may also follow up with caregivers who participated in CONFIDENCE but did not enroll in the research study to conduct qualitative interviews. The process for these interviews are consistent with those used for caregivers enrolled in the parent study. We will use purposeful sampling according to engagement in the program (e.g., attended all four sessions).

**NeuViCare Utilization data.** Data on app utilization will be available on a dashboard viewable to the study team and facilitator on the NeuViCare App. They PI will be able to view and record data stored in the secure NeuViCare Google Cloud on a secure dashboard using a unique login. Aggregated information on Care Advisory search subject will be shared by email; that is, we will not see questions individuals submitted to Keiko.

**Payment.** Participants will receive up to \$160 for their participation using emailed Amazon Gift Cards. They will receive \$50 for the baseline survey completion and \$50 and \$60 for the first and second follow-up survey, respectively.

**Fidelity monitoring.** Fidelity will be monitored using a form developed for the initial CONFIDENCE intervention with additional refinements from talking to interventionists. This form will be completed by an observer who views a video recording of selected sessions. Questions will be based on adherence to the session agenda, timing, participant experience, and quality of delivery. One session per cohort will be randomly selected for fidelity monitoring.

**Attendance.** Attendance to each session will be recorded by facilitators and shared with Case Western using a Box folder. The average number of sessions attended by participants and the standard deviation will be reported and compared between the English and the Spanish sessions. Another comparison, in the form of percentage based on the different number of possible sessions to attend, will be made on attendance between CONFIDENCE vs CONFIDENCE.

**Participant safety monitoring.** *Confidentiality.* All survey data will be de-identified and only the PI will have access to the identifier information. NeuViCare user data will be tracked using an email address and phone number. Only the PI will have access to the study key that will allow link study data to contact information, and will not share this with other study team members to prevent breach of privacy. *Transient emotional distress.* If caregivers experience emotional distress while interacting with a study team member, they will be referred to resources of self-care, community support and the Alzheimer's Association 24/7 Helpline. **Adverse events.** All suspected study adverse events will be reported using a standardized form in REDCap. These will be tracked and monitored by the PI. All study team members will be trained to identify on risk management protocols, such as when to immediately contact the PI about a suspected adverse event. See the Adverse Event Form.

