## 5.0 Number of Research Participants

**Directions: Indicate the target number of research participants to be accrued locally, and, if this is a multi-site study, indicate the total number of research participants to be accrued across all sites.**

**Example language that can be used:** *We will enroll 25 subjects at CWRU and plan to enroll 150 subjects study wide.* We will recruit 42 family caregivers to account for the anticipated 20% attrition before and after participation in CONFIDENCE 2. Moreover, at least 12 participants will complete qualitative interviews.

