The anticipated recruitment period will begin in March 2024 to August 2025. We aim to enroll 5-6 caregivers per cohort. Each cohort will take 4-5 weeks to complete. We aim to use the same recruitment approach as was done in the original CONFIDENCE study, relying heavily on the USC FCSC client list. USC FCSC serves over 500 caregivers yearly, among whom 60% are Latino/Hispanic and 38% care for someone living with AD/ADR. Although recruitment into the initial study was far lower than anticipated, multiple factors are expected to contribute to higher enrollment in this study, including 1) reduced burden of participation in the intervention (e.g., reduction of synchronous sessions from 5 to 4), 2) reduced burden of study participation (e.g., removal of daily spending diary component), and 3) expansion of age eligibility criteria from caregivers ages 50+ to 18+ in the current study. Further, we have expanded our recruitment approach during the initial CONFIDENCE study.

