**Satisfaction surveys.** To analyze Likert responses to satisfaction surveys, a percentage for each response will be provided. Each item will be compared to items collected for the initial CONFIDENCE study, as well as scores for items of CONFIDENCE between Spanish and English intervention.

**Attendance.** We will report the average number of sessions attended (range 0 to 4) and the standard deviation. Comparison on the number of sessions attended will be compared between the English and the Spanish sessions as well as between the earlier and current version of CONFIDENCE in the form of percentages to allow us to draw preliminary comparisons, given the different number of possible sessions to attend (3 vs. 5). The average number of sessions will be calculated both with and without accounting for make-up sessions. (i.e., giving credit for attendance in Session 1 if the caregiver attended the makeup session for this lesson.)

**App Utilization.** Usage data from NeuViCare™ Care and Resources Advisors will be reported in aggregate Individual-level data will be collected on the average number of text received, average interactions on the Community Hub, and average number of practice activities completed on NeuViCare.

**Fidelity.** Fidelity reports will be evaluated using total scores averaged across all CONFIDENCE sessions observed. Sub scores will be reported for adherence to the facilitator guide, participant experience, and quality of delivery. These will be reported separately for English and Spanish participants by using a percentage, as well as means and standards of deviation, to examine variability.

**Qualitative interviews.** Qualitative interviews will be transcribed verbatim, and for the ones conducted in Spanish, they will be previously translated. Transcription and translation of interviews conducted in Spanish will be by ASTA-USA. English Transcriptions will be done by GMR. A preliminary code book will be developed by at least two research members and will be refined prior to applying codes to the remaining interviews. At least two coders will analyze each transcript independently and will meet to compare the codes. The second round of coding will be conducted to integrate new codes if needed.

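### The fidelity session is drawn at random in each cohort with no stated balancing, so one of the four sessions may well go unobserved, overall and especially within a language

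*Combined protocol and SAP*

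**What the plan says.** Section 12.0, under fidelity monitoring, sets the sampling rule: "One session per cohort will be randomly selected for fidelity monitoring". An observer completes a form from the video recording, covering agenda adherence, timing, participant experience and quality of delivery. The same section describes the programme: "The intervention includes participation in four, 1.5 hour group discussion sessions", and "CONFIDENCE will be delivered in English and Spanish".

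Section 17.0, under fidelity, gives the summary: "Fidelity reports will be evaluated using total scores averaged across all CONFIDENCE sessions observed". Sub-scores follow, and then: "These will be reported separately for English and Spanish participants". The stated form is percentages, means and standard deviations, to look at variability. There is no adjustment for session number, no test and no contrast between languages.

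The number of cohorts is not stated. It follows from Section 8.0, "We aim to enroll 5-6 caregivers per cohort", and Section 5.0, "We will recruit 42 family caregivers to account for the anticipated 20% attrition".

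**The concern.** One session in four is seen per cohort, and there are few cohorts. Unless the draw is balanced, the same session number can come up repeatedly while another is never seen. A session that is never observed has no fidelity evidence at all, yet the overall average would be read as describing the whole programme. That matters somewhat here, because feasibility is a stated objective and the programme has been restructured from five sessions to four.

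The problem is sharper within a language, where the number of draws is about half as large. The English and Spanish averages would then usually rest on different sets of sessions, and the planned summary does not show which. If fidelity differs by session, part of any visible gap between the two columns would reflect which sessions were drawn.

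**Working it through.** The documents give no figure for fidelity coverage, so there is nothing to reproduce. The check derives coverage from their own inputs.

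**Inputs**
- Sessions per cohort: 4 (Section 12.0; the attendance range of 0 to 4 in Section 17.0 agrees).
- Enrolment: 42 (Section 5.0).
- Cohort size: 5-6 (Section 8.0).
- Observed sessions per cohort: 1 (Section 12.0).
- Assumptions: draws are independent with equal probability; each cohort runs in one language; the language split, which is not stated, is roughly even at 3 to 5 cohorts each.

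**Number of cohorts.** 42/6 = 7 and 42/5 = 8.4, so 7 to 9.

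**Coverage.** With k cohorts, the probability that at least one of four sessions is never drawn is

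P(miss) = 4(3/4)^k − 6(1/2)^k + 4(1/4)^k.

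All cohorts together:
- k = 7: 0.5339 − 0.0469 + 0.0002 = 0.487
- k = 8: 0.4005 − 0.0234 + 0.0001 = 0.377
- k = 9: 0.3003 − 0.0117 + 0.0000 = 0.289

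Within one language:
- k = 3: certain, since three draws cannot cover four sessions
- k = 4: 1.2656 − 0.3750 + 0.0156 = 0.906
- k = 5: 0.9492 − 0.1875 + 0.0039 = 0.766

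Both languages cover all four sessions with probability 0 for a 3+4 split, 0.0938² = 0.009 for 4+4, and 0.0938 × 0.2344 = 0.022 for 4+5.

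**Difference in session mix between languages.** The measure is half the sum, over the four sessions, of the absolute difference in the share of observations: 0 means identical mixes, 1 means no overlap. Expected values are from full enumeration of the draws.

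| Cohorts per language | Independent draws | Without replacement within language |
|---|---|---|
| 3+4 | 0.52 | 0.25 |
| 4+4 | 0.46 | 0.00 |
| 4+5 | 0.46 | 0.15 |
| 3+5 | 0.51 | 0.30 |

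The 3+4 balanced value can be checked by hand: ½(3 × |1/3 − 1/4| + |0 − 1/4|) = ½(0.25 + 0.25) = 0.25. Under independent draws the expected signed gap in mean session number is exactly zero for every split.

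**Sensitivity.** More, smaller cohorts reduce the overall problem: P(miss) is 12.5% with 12 cohorts and 4.0% with 16. The attendance paragraph of Section 17.0 also contrasts three with five possible sessions, which conflicts with four sessions elsewhere and should be reconciled. With three sessions, P(miss) = 3(2/3)^k − 3(1/3)^k, or 17.4%, 11.7% and 7.8% for 7, 8 and 9 cohorts: smaller, but in the same direction.

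**The case against.** Several counter-arguments have force.

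- A reader might infer that an English-Spanish fidelity comparison is confounded with session number. The documents do not support that. Section 17.0 plans separate descriptive reporting of fidelity, whereas for attendance and satisfaction it does name a comparison between languages. Random selection also gives every session the same chance in both languages, so what arises is chance imbalance and not bias. This objection stands in full.
- Nothing shows that fidelity differs by session. Agenda adherence and timing are judged against each session's own agenda, so a difference is plausible, but no session-level scores are given. Any figure in points for a spurious language gap would rest on invented session means. This stands too. It does not touch coverage: an unobserved session is unobserved whatever its fidelity.
- The wording says the session is chosen at random; it does not say the draws are independent, and it does not exclude a balanced list. True. The percentages above apply only to independent draws, and the gap is then that the rule is not specified.
- The cohort count and language split are inferred. With 8 or 9 cohorts, full overall coverage is more likely than not. Fair, and the range is shown for that reason.
- Balancing is not a complete cure. A language with three cohorts still misses a session, and one observation per session and language leaves facilitator and cohort variation in place.
- The protocol is dated 19 May 2025 and recruitment was planned from March 2024 to August 2025, so some cohorts may already have run. This limits what a new list can achieve but does not remove the reporting part of the fix.

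**Conclusion.** The point holds as a modest, optional improvement. As written, the rule does not secure observation of all four sessions. With independent draws and 7 to 9 cohorts, at least one session is missed overall in 49% to 29% of realisations. Within a language of 3 to 5 cohorts, it is missed in 100% to 77%. The language-specific averages would therefore usually describe different session mixes, and the plan does not ask for that to be shown.

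This rests on independent draws, single-language cohorts, a roughly even language split and cohorts of the planned size. Whether the mix moves the scores at all depends on variation in fidelity between sessions, on which the documents are silent. Fidelity is a process measure and is not among the listed outcome measures, so the analyses of resourcefulness, self-efficacy and financial strain are unaffected.

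**What to change.** In Section 12.0, replace the selection sentence with wording such as:

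*For each cohort, the session to be observed will be taken from a pre-generated list, concealed from facilitators, that draws session numbers 1-4 in random order without replacement within each language, restarting after every four cohorts. For cohorts still to run, sessions not yet observed in that language will be drawn first.*

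In Section 17.0, add that the session numbers observed in each language will be reported, and that the language-specific fidelity results are descriptive. If no cohorts remain, this addition is the whole fix.

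Used from the first cohort, such a list covers all four sessions in any language with at least four cohorts. With 7 or more single-language cohorts in two languages, at least one language must have four, so overall coverage is then assured. A language with fewer than four cohorts will still miss at least one session, and the report should say which.

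The cost is two short edits and a list to maintain, with the same number of recordings and the same rater time. The one drawback is that the last session in each block is predictable if the list is not concealed.
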